Acute intake of doses > 10 times the maximum therapeutic dose has been reported. In addition to those events reported as Undesirable Effects, overdose has resulted in symptoms including drowsiness, loss of consciousness and/or ECG changes such as conduction disturbances (including QRS prolongation), arrhythmias and tachycardia. QTc prolongation has also been reported but was generally seen in conjunction with QRS prolongation and increased heart rate. Most patients recovered without sequelae, yet there are some rare reports of deaths associated with BUP in patients ingesting large overdoses of the drug. The use of

activated charcoal is recommended. No specific antidote for BUP is known. In the event of overdose, hospitalization is advised and management should be as clinically indicated.

CYP2D6 inhibition by BUP and hydroxy-BUP

Although not metabolised by the CYP2D6 isoenzyme itself, BUP and its main metabolite, hydroxybupropion, inhibit the CYP2D6 pathway and may thus increase the effect of certain drugs. *Action taken to prevent drug drug interactions:* To mitigate pharmacokinetic interactions, concomitant medication with drugs metabolized via CYP2D6 will be avoided as medical conditions requiring these drugs are exclusion criterias. (See prohibited medication, certain antidepressants and type 1 antiarrhythmics. For full list of interactions, see SmPc, Attachments 2.)

Pharmacokinetic interactions between varenicline and bupropion

VAR and BUP have no known clinically significant drug drug interactions. VAR does not change the pharmacokinetics of BUP at steady state and vice versa, there are no reports that BUP alters the excretion of VAR (92-93% excreted by the kidneys). BUP and its main active metabolite, hydroxybupropion, inhibit the CYP2D6 enzyme. *Action taken to minimize drug drug interactions:* According to clinical data, there are no pharmacokinetic interactions between BUP and alcohol. The SmPC for BUP states that there are a few reports on neuropsychiatric side effects and decreased tolerance to alcohol with BUP.

Elderly population

This trial includes subjects up to 70 years, whereof those between 65-70 years are classified as elderly (WHO definition is people aged 65 and over). This age group has a higher risk for reduced liver and kidney performance, and consequently a lower dose may be appropriate in some subject, as outlined in the SPC. It is the Sponsor's judgment that dose reduction is not needed in this trial, despite including subjects up to age 70. For the purpose of safety, liver (by AST, ALT and PC) and kidney (by creatinine) status will be monitored before, during and after the treatment period.

Expected side effects and medical risks of varenicline and bupropion used in combination

In nicotine dependence, the safety profile of VAR and BUP in combination has been described in six studies (seven publications). In these studies, VAR was investigated in the dose of 1 mg twice daily and BUP in the dose of 150 mg twice daily (Except for study 4, where BUP was dosed as 150 mg once daily). Both drugs were titrated during the first week according to recommendations.

Reference study 1

VAR and BUP sustained-release combination therapy for smoking cessation (Ebbert et al., 2009). This was an open-label, one-arm, phase II pilot study with 38 enrolled subjects lasting 12 weeks with 6 months follow up. The study evaluated the combination as safe. The most common reported AE of combination therapy were sleep disturbance (26%), nausea (24%) and insomnia (16%). The study excluded active AUD but not alcohol consumption as such. Efficacy outcome variable: prolonged abstinence at 12 weeks and at follow-up 6 months. Results showed 63% prolonged abstinence at 12 weeks and 53% at 6 months in the combination treatment group.

Reference study 2

Combination treatment with VAR and BUP in an adaptive smoking cessation paradigm (Rose and Behm, 2014). RCT, N=349. This was a 12-week randomized, adaptive treatment, double-blind phase III clinical trial. The study evaluated the combination as safe. The most common reported AEs of combo therapy were headache (9.3%), diaphoresis (8.8%), nasal/sinus irritation (5.9%), changes in taste perception (17.2%), dry mouth (10.8%), thirst (15.7%), cough (8.8%) irritability (11.3%), vivid dreams (18.1%), insomnia (13.7%) and anxiety (8.8%). The study excluded AUD but not alcohol consumption as such. Efficacy: Outcome variable continuous abstinence at week 8-11. Combination therapy increased abstinence relative to varenicline monotherapy (39% vs 26%), OR 1.89. Male smokers had a greater effect than females; OR 4.26 vs 0.94. Highly dependent smokers had a greater effect; OR 3.51 vs 0.71.

Reference study 3

Combination VAR and BUP SR for tobacco-dependence treatment in cigarette smokers: a randomized trial (Ebbert et al., 2014). This was a 12-week randomized, blinded, placebo-controlled phase III clinical trial. RCT, N=506. The most common reported AEs of combination therapy were sleep disturbances (40.2%), nausea (22.1%), constipation (10.4%), anxiety (7.2%) and depressive symptoms (3.6%). The study excluded AUD but not alcohol consumption as such. Efficacy: N=506, RCT, outcome variable prolonged abstinence at 12 weeks and 26 weeks. At 12 weeks Odds Ratio for varenicline monotherapy was 1.36 and for combination therapy combination 1.49. At 26 weeks monotherapy varenicline OR 1.32 vs OR 1.52 for the combination therapy. At 52 weeks OR 1.40 for varenicline monotherapy and 1.39 for the combination therapy.

Reference study 4

Effectiveness of co-administration of VAR, BUP, and serotonin reuptake inhibitors (SRI) in a smoking cessation program in the real-life setting (Issa et al., 2013). N=427. This was a retrospective outcome research study of patients that received VAR, VAR+BUP, VAR+SRI or VAR+BUP+SRI and were followed during 1 year. AEs were not collected in the study but nausea and abnormal dreams were reported as bothersome and primary reasons for treatment failure (15.2% of treatment failure group). Efficacy: retrospective data on consecutive patients receiving treatment. Outcome variable continuous abstinence at 52 weeks. For the combination therapy of VAR and BUP the success rate was higher than for VAR monotherapy; 55% vs 32%, OR 3.21.

Reference study 5

Combination VAR/BUP treatment benefits highly dependent smokers in an adaptive smoking cessation paradigm (Rose and Behm, 2017). N= 122+52, RCT. This was a randomized double-blind, parallel group, adaptive treatment trial that identified 222 cigarette smokers not responding to pre-quit nicotine patch treatment, that received VAR/BUP or VAR/placebo for 12 weeks. Combination treatment was more efficacious than VAR alone among highly dependent male smokers. Overall, both treatments were well tolerated; 11.5 % required dose reductions in the VAR/BUP group and 24.8% in the VAR group. The incidence of AE did not differ between the groups. The most common AE in the VAR/BUP group were vivid dreams 14.9%, irritability (9.2%), dry mouth (9.2%) and insomnia (8.0%). Seven participants (4 in the combination arm and 3 in the VAR arm) dropped out due to AEs likely related to treatment. Male smokers and more highly dependent smokers showed the greatest therapeutic response. It was not reported that AUD was a feature for exclusion. Efficacy: outcome variable continuous abstinence at week 8-11. For highly dependent smokers (FTND score 6 and more, cigarettes 20 and more), but not lower dependency smokers, combination therapy was superior to varenicline monotherapy in increasing abstinence; OR 3.14.

Reference study 6

Depressive symptoms among patients receiving VAR and BUP for smoking cessation (Hong et al., 2015). N=385. This was a subsequent analysis of the Phase III trial conducted by Ebbert (Ebbert et al., 2014), study 3 above. It was reported that combination therapy with VAR and BUP increased depressive symptoms over the first 2 weeks but this did not last beyond 4 weeks.

Reference study 7

In the most recent published RCT with the combination of VAR and BUP, contrary to previous studies, the addition of BUP to VAR did not increase the efficacy on smoking abstinence (Cinciripini et al., 2018). Compared to placebo, the group receiving both VAR and BUP showed decreased appetite and increased dry mouth, insomnia, dysgeusia, creatinine and edema. It should be noted that pre-existing medical conditions may have caused elevations of creatinine, edema and dysgeusia. One SAE, which involved a suicide attempt, was rated as possibly related to VAR, although there were other factors surrounding the event. Efficacy outcome variable: prolonged abstinence at 12 months. Odds Ratio for VAR monotherapy, compared to placebo was 6.66. Odds ratio for combination treatment VAR and BUP, compared to placebo was 6.06. There was no BUP monotherapy group. The combination therapy was superior to VAR monotherapy only in smokers with 6 or more scoring at the Fagerström Test for Nicotine Dependency (35% vs 16%, OR 2,81).

Varenicline and bupropion interactions with alcohol

VAR is already tested in subjects with AUD and the interaction with alcohol was found not to be clinical significant (Litten et al., 2013;de Bejczy et al., 2015). In the clinical trials with the combination VAR and BUP, AUD patients have been excluded. However, alcohol-consuming patients were not excluded and alcohol consumption was not an exclusion criteria. No adverse interactions were described (reference studies 1-7 above). Drugs of abuse, including alcohol, enhance DA levels in the brain. Both BUP and VAR increase DA levels in the reward region of the brain. However, BUP and VAR have a slow onset of action and a much lower increase in DA levels and are not judged to have an addictive potential. According to Läkemeldesverket, no reports of addiction to VAR or BUP have been reported (oral communication). The combination of alcohol, VAR and BUP have a theoretical risk of enhancing alcohol's effects and producing a high/false sense of well-being (Volkow and Swanson, 2003), although no such effects were observed in the VAR studies on alcohol. The known increase risks for seizures have been minimized by the exclusion criteria of Epilepsy and alcohol seizures (within 5 years) and need of detoxification. The risk for worsening symptoms of other psychiatric disorders has been minimized by the exclusion criteria. Common side effects of VAR and BUP include e.g. insomnia, dizziness, nausea, all of which are associated with alcohol consumption. These symptoms could possibly be more frequent in the case of VAR, BUP and alcohol in combination.

Risks associated with study specific examinations and sampling

Venous blood will be collected for investigation of eligibility measures and/or outcome measures and/or safety measures at every study visit (9 in total) by professional medical staff (See table 2, section 3.1 for specific investigations). The blood will be drawn from the upper or lower arm. The total amount of blood taken during the whole study will be 245 mL. It is rare for a blood test to result in serious complications but there is a small risk for complications like infections, excessive bleeding, bruising, fainting and dizziness and hematomas. *Action taken to control or minimize above described risks.* Infection control during blood sampling: the medical staff is highly trained and is required to follow the regulations regarding the disposal and storage of needles and blood samples. In rare cases, a wound occurs that become red and swollen, and if

so the subject is referred to appropriate medical care. Bleeding and bruising control: if bleeding occurs this will be stopped quickly by placing a cotton wool pad or gauze patch on the wound. Mild pressure on the site after removal of the needle will minimize the bleeding which will reduce the risk of bruising. *Fainting and dizziness control.* Some people experience dizziness during or after a blood test. If the subject is feeling faint before or during a blood test, he/she is offered to lie down on the examination bench. This will increase blood flow to the brain and counteract fainting.

7.2. Definitions

7.2.1. Adverse Event (AE)

An AE is any untoward medical occurrence in a patient or clinical investigation subject administered a medicinal product and which does not necessarily have a causal relationship with this treatment. An AE can be any unfavorable and unintended sign (including an abnormal laboratory finding), symptom, or disease temporally associated with the use of the IMP, whether or not related to the IMP.

Causality

The Investigator is responsible for determining whether there is a causal relationship between an AE and the use of a medicinal product.

All AEs are categorized either as unrelated, possibly related or related, as defined below:

- Unrelated: the AE is not reasonably in relation to the use of the IMP, or another cause can itself explain the occurrence of the event.
- Possibly related: the AE may be explained by an effect of the IMP and the onset is reasonable in relation to the use of the medicinal product, however there is insufficient information to determine the likelihood of this possibility.
- Related: the AE is most likely explained by the IMP and the onset is reasonable in relation to the use of the medicinal product (see 7.2.2., ADR).

Severity

In addition to assessing the relationship of the administration of the IMPs to adverse events, an assessment is required of the intensity (severity) of the event. The following over-all classification will be used:

- Mild: An adverse event which is relatively mild and transient in nature, but can be an annoyance, and does not interfere with normal activities.
- Moderate: An adverse event which may be uncomfortable but is not hazardous to health. It may be sufficiently discomforting to interfere with normal activities but does not completely prevent them.
- Severe: An adverse event which is incapacitating and/or is a hazard to the subject

Definition of action taken

Action taken will be defined as

- None. No action will be taken
- Due to the AE, interruption in IMP administration
- IMP discontinued. Due to the AE, the patient's IMP administration will be discontinued.
- Trial discontinuation
- Others (like referrals)

Definite event outcome at resolution or End of Trial

- Resolved without sequelae
- Resolved with sequelae
- Not resolved
- Fatal
- Unknown (if lost to follow up)

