Seizures. BUP has been shown to increase the risk of seizures. The seizure threshold decreases on abrupt cessation of excessive drinking, thus seizures may occur during withdrawal (6-48 hours after the cessation of drinking). The relationship of seizures to alcohol use is likely to be dose dependent and causal (Hillbom et al., 2003). Available clinical data suggest that excessive alcohol drinking is contraindicated for BUP (SmPC BUP, Attachment 2). In this trial, there will be no abrupt cessation of alcohol intake and subjects with a previous history of seizures are excluded. It is therefore the Sponsor's judgment that there will be an equal or even lower risk of seizures in this trial compared to the approved indication. If however, a seizure occurs, it will be considered and reported as SAE and the subject will immediately be withdrawn from the study and referred to appropriate medical care. The Investigator will follow up the subject until treatment termination and notify the outcome to the Sponsor. *Action taken to mitigate or minimize the risks of eliciting seizures during BUP administration:* Subjects will be screened for lifetime incidence of seizures, which is a criterium for exclusion. The absence of a history of seizures will be confirmed through collection of medical history during prescreening and during screening. To mitigate or minimize alcohol withdrawal that may predispose for seizures, subjects will be screened for a periodic pattern of alcohol consumption that is a criterium for exclusion. If a seizure occurs during the trial the study subject will immediately be excluded from the trial (see exclusion criteria).

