7.3.2. Adverse Drug Reaction (ADR)

AEs considered related to the trial medication as judged by the medically qualified investigator or the Sponsor will be followed either until resolution, or the event is considered stable.

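### The definition of an unrelated adverse event in 7.2.1 is met by any other cause sufficient to explain it, which in heavy drinkers permits genuine drug reactions to be coded unrelated

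*Protocol*

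**What the plan says.** Section 7.2.1 sets a three-level causality scale: "All AEs are categorized either as unrelated, possibly related or related, as defined below". An event is unrelated if "the AE is not reasonably in relation to the use of the IMP, or another cause can itself explain the occurrence of the event". It is possibly related if "the AE may be explained by an effect of the IMP and the onset is reasonable" in relation to use of the product, with the further condition that there is too little information to judge how likely this is. It is related if the product most likely explains it; that entry points to section 7.2.2.

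Section 7.2.2 defines an adverse drug reaction by a reasonable causal relationship, and says evidence or an argument pointing to causality is enough. Section 7.3.2 adds: "AEs considered related to the trial medication as judged by the medically qualified investigator or the Sponsor will be followed either until resolution", or until stable.

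On the events themselves, section 7.1 says: "Common side effects of VAR and BUP include e.g. insomnia, dizziness, nausea, all of which are associated with alcohol consumption". On seizures it says both "BUP has been shown to increase the risk of seizures" and "The seizure threshold decreases on abrupt cessation of excessive drinking, thus seizures may occur during withdrawal".

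**The concern.** The two conditions for *unrelated* are alternatives. The second, "or another cause can itself explain the occurrence of the event", asks whether something else could account for the event by itself. It does not ask whether that explanation is the more likely one, or whether the study drug may also have contributed.

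In many trials this would matter little. Here the competing cause is a condition of entry, and the protocol names it for the same events that it expects from the drugs. It is also the setting in which attribution is least settled: section 7.1 reports no controlled trial of bupropion in alcohol-dependent subjects, and says the combination trials excluded patients with alcohol use disorder.

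At stake are the relatedness code, what counts as an adverse drug reaction, the follow-up that depends on it, and consistency of coding between physicians and centres.

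**Working it through.** No figure in the plan is to be reproduced here. The check is a comparison of sections, with one supporting calculation.

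**1. Is the second condition sufficient alone?** Yes. It is joined to the first by *or*, and its verb is *can*. An event with plausible timing and a known drug effect still meets it if another cause could produce the event unaided.

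**2. Is such a cause available?** At entry, yes. The synopsis requires B-PEth of at least 0.5 µmol/L and at least 2 heavy drinking days in a typical week. Section 4.2 excludes anyone totally abstinent between screening and randomization. Heavy drinking is thus assured at entry, though not throughout treatment.

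**3. Do the drug effects and alcohol effects coincide?**

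| Event | As a drug effect | As an alcohol effect |
|---|---|---|
| Insomnia, nausea, dizziness | Section 1.2 lists them among the main expected events of the combination | Section 7.1 associates all three with alcohol consumption |
| Seizure | Section 7.1, as a bupropion risk; section 1.2, as a main medical concern | Section 7.1, as a withdrawal event |

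**4. Are the categories exclusive?** Not fully. Take nausea in week 1 in a participant who is still drinking. The drug may explain it, the onset fits, and the information may not settle the likelihood, so *possibly related* applies. If the physician also judges that alcohol could explain it alone, *unrelated* applies too. Section 7.2.1 does not say which prevails.

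**5. Is 7.2.1 consistent with 7.2.2?** No. Under 7.2.2 an argument for causality is enough, with no exception where another cause exists. The nausea in step 4 could be an adverse drug reaction under 7.2.2 and unrelated under 7.2.1. In addition, 7.2.1 refers to 7.2.2 only from the *related* category, so it is unclear whether a *possibly related* event counts as an adverse drug reaction.

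**6. Are genuine reactions at stake?** Section 7.1 gives nausea rates, varenicline versus placebo, from two trials in alcohol use disorder. The share of varenicline-arm nausea above the placebo rate is (varenicline rate − placebo rate) / varenicline rate:
- Swedish trial: (48.1 − 12.0) / 48.1 = 36.1 / 48.1 = 75%.
- US trial: (37.1 − 17.8) / 37.1 = 19.3 / 37.1 = 52%.

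In this population, then, half to three quarters of nausea on varenicline is above background. These shares show that the events are largely real reactions. They do not predict how many would be miscoded.

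**7. What depends on the code?** Follow-up under 7.3.2 does. So does the provision in 7.1 for relieving nausea, which applies only where the nausea is judged possibly related to the product.

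**The case against.** The case against has real weight. The word *itself* sets a bar: alcohol must be enough alone, and its mere presence in every participant does not meet that. *Possibly related* carries the insufficient-information condition, which makes it the natural home for doubtful cases. The protocol also leans that way in places: 7.1 foresees nausea coded as possibly related, suggests these symptoms may be more frequent when both drugs and alcohol are combined, and expects no abrupt stop to drinking. The sponsor as well as the investigator may judge a reaction under 7.2.2.

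These points narrow the overlap but do not close it. Alcohol or withdrawal can be sufficient alone for each listed event, and sufficiency of one cause does not exclude a contribution from another. An event to which both drug and alcohol contribute, as 7.1 anticipates, is the kind the second condition can misclassify.

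A reader might infer four stronger things that the document does not support.
- **That reactions will be lost from the safety data.** Section 7.3.1 records every event whether or not it is attributed to trial medication. Section 8.2 summarizes safety descriptively by treatment group, and the protocol plans no by-arm analysis based on relatedness.
- **That seizures could go unreported.** Section 7.1 makes any seizure a serious adverse event whatever its code, and 7.2.4 says a SUSAR may be related or unrelated.
- **That follow-up would lapse altogether.** Sections 3.3 and 4.4 provide calls after treatment or discontinuation, and 7.3.1 provides care to resolution or stability for those who stop because of an event.
- **That all nausea reactions in an arm could vanish from the count.** That would need every physician to code every case the same way. It is a logical limit and says nothing about what is likely.

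**Conclusion.** The point stands as a defect in a stated rule. Section 7.2.1 permits, but does not compel, a genuine reaction to be coded unrelated because drinking or withdrawal could account for it. It leaves an overlap with *possibly related* unresolved, and it sets a different standard from 7.2.2.

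The effect is limited to relatedness codes, identification of adverse drug reactions, follow-up under 7.3.2, and the nausea provision in 7.1. Comparisons of all events by randomized arm, serious-event reporting of seizures and SUSAR status are untouched. No count of miscoded events can be given, since it depends on how physicians apply the rule. The 52% to 75% share rests on the two earlier trials' rates applying to similar patients, and shows only that true reactions are among the events exposed.

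This should be corrected: the rule is written down, it is open to inconsistent use across centres, and repair is nearly free.

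**What to change.** In 7.2.1:
- Reserve *unrelated* for events where a contribution of the study product can reasonably be excluded.
- State that another possible cause, including drinking or alcohol withdrawal, is not enough by itself for that code.
- State that *possibly related* prevails when an event fits both categories.

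Reconcile 7.2.1 with 7.2.2 so that one standard governs, and say whether a *possibly related* event is an adverse drug reaction for 7.3.2. Check that the nausea provision in 7.1 still reads as intended once the categories are settled.

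The cost is a few sentences in the protocol and the same wording in the case report form instructions. No visit, dose or endpoint changes. The downside is that more events will be coded *possibly related*, in all arms including placebo.
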